The EMS Sleep Health Study: A Randomized Controlled Trial

Study Protocol including Statistical Analysis Plan

Supported by the National Highway Traffic Safety Administration (NHTSA)
Contract#: DTNH2215R00029

The study was supported in concert with the National Association of State EMS
Officials (NASEMSO)

Research Study Principal Investigator: P. [name], NRP;
University of Pittsburgh Department of Emergency Medicine;
Project Lead for NASEMSO: [name]

University of Pittsburgh Institutional Review Board (IRB) # STUDY19080090;
(Initial IRB approval date: 10/4/2019; last modification approval date: 11/4/2020);
Office of Management and Budget [Control Number: 2127-0742; ICR Reference
Number: 201811-2127-003; approved on 8/2/2019]; and registered on
ClinicalTrials.gov (NLM Identifier: NCT04218279)

Table of Contents

Background and Specific Aims	Page 3
Overview of Methods	Page 4
Study site	Page 5
Recruitment methods	Page 6
Compensation / remuneration offered to participants	Page 7
Study design (including power analysis and analysis plan)	Page 8
Consent procedures	Page 13
Data safety monitoring	Page 14
Protecting privacy	Page 15
Termination, withdrawal, or attrition	Page 16

Background and Specific Aims

Problem:

Greater than half of EMS personnel report poor sleep quality and fatigue. The odds of injury, medical error, and adverse events are higher among EMS personnel who report fatigue and poor sleep. There are few evidence-based interventions tailored to EMS workers that may improve sleep and reduce fatigue.

Significance:

A recent review of the published evidence shows that education and training tailored to the EMS personnel may reduce fatigue and improve safety on the roadways.

Specific Aims:

The purpose of the proposed study, is to measure the extent to which education and training in sleep health and fatigue will benefit EMS personnel and to explore the effects of a novel education intervention on EMS personnel. The study's two primary outcomes of interest include: [1] sleep quality as measured by the Pittsburgh Sleep Quality Index (PSQI); and [2] fatigue as measured by the Chalder Fatigue Questionnaire (CFQ).

Hypothesis:

Overview of Methods

We will use an experimental study design with a wait-list control group. We seek to enroll a maximum of 40 EMS agencies nationwide and approximately 10-to-50 individual EMS personnel from each agency. All agencies and individuals enrolled in this study will participate voluntarily over a six-month study period.

Study site:

University of Pittsburgh main campus

The University of Pittsburgh Department of Emergency Medicine has the necessary personnel and computer equipment, as well as software, to fulfill the study's aims. The Department of Psychiatry WPIC Office of Academic Computing is a partner in this project and has demonstrated, in numerous studies, to have the necessary personnel, expertise, computer equipment, and software needed to fulfill the study as designed.

Recruitment methods:

Members of the study team will use telephone and email communication to communicate with the EMS agency directors and individual EMS clinicians. Study team members will include the PI, co-investigators, and study coordinators / staff.

Methods for recruitment:

- Directly approaching potential subjects (in-person)
- Email/Listserv/Electronic Mailing List
- Flyers/Posters or Brochures
- Telephone scripts
- Website/Social Media

Details of recruitment methods:

We will use study flyers and standardized emails to first recruit EMS agency directors to participate in this study. Once an agency has agreed to participate, we will then ask the agency administrator to distribute a paper-based study flyer and standardized recruitment email to their EMS crew/staff via their email lists. We will also ask the administrators to post a paper-based version of the study flyer in high traffic areas of the EMS organization. Any representative of an EMS agency who comes across our study website (<https://www.emssleephealth.pitt.edu>) may wish to communicate with the study team about participation.

We also have video-based versions of study flyers. We will use the following methods to circulate these flyers:

[1] For the video-based version of the Agency Level Research Study Flyer, we will host the video version of the research study flyer on our study website. Agency directors who come into contact with our paper-based study flyer will be directed to view the video version on the study website, which we will keep password protected.

[2] For the video-based version of the Individual Level Research Study Flyer, we will ask the agency directors/administrators who have agreed to participate in our research study to circulate this video-based version on their internal email list-serve or internal computer system in a method similar to circulating the paper-based version.

Compensation / remuneration offered to participants

Our remuneration plan for study participants will include \$5.00 (five dollars) to sign up/enroll, followed by \$5.00 (five dollars) each month for the six-month study period. If a study participant completed the study as designed (6 months), he/she will receive a total of \$35 total dollars.

Those who participate in this research study will have the opportunity to apply for 2.25 hours of continuing education credits offered by the Commission on Accreditation for Prehospital Continuing Education (CAPCE). The National Association of State EMS Officials (NAEMSO) will be the responsible for processing your individual application of continuing education. The information needed to apply for these continuing education credits will be available on the study website. Please see the attached letter from the NASEMSO regarding their role/responsibility in managing the continuing education credit processing.

Study design

Total number of subjects to be enrolled = 1500

Describe and explain the study design:

We will use an experimental study design with randomization at baseline and use of a wait-list control group. This design will ensure that all study participants receive the intervention, which may have significant benefits to EMS agencies and individual participants in terms of sleep quality and fatigue.

We will convenience sampling to recruit nationwide for EMS agencies. Moderately sized EMS organizations with (on average) between 50 + employees (EMS personnel) will be eligible to participate.

This approach will increase the likelihood of meeting enrollment goals by maximizing visibility of the study to as many EMS organizations as possible. Threats to external validity are limited due to the high degree of homogeneity of the EMS workforce (e.g., mostly male, middle aged, and mostly certified at the EMT-Basic level). All enrolled EMS organizations will be ground-based EMS operations; air-medical ONLY services will be excluded; however, dual air-medical/ground services may be eligible to participate. The sample will include dual fire-EMS operations as well. Participation from EMS organizations located in all U.S. Census regions will be achieved with nationwide recruitment. The study is powered to detect change in two outcomes of interest: [1] sleep quality as measured by the Pittsburgh Sleep Quality Index (PSQI); and [2] fatigue as measured by the Chalder Fatigue Questionnaire (CFQ). Maximum goal enrollment is set at n=40 EMS organizations.

Primary and secondary outcomes:

The study is powered to detect change in two outcomes of interest: [1] sleep quality as measured by the Pittsburgh Sleep Quality Index (PSQI); and [2] fatigue as measured by the Chalder Fatigue Questionnaire (CFQ).

Timeline:

Duration of an individual subject's active participation: Six months, plus up to one month that may be needed to process enrollment and close-out procedures for the EMS agency to which the individual participant is affiliated.

Inclusion criteria for EMS agencies:

The researchers will recruit EMS nationwide for EMS agencies to participate in this study. Moderately sized organizations with between 50 and 300 employees will be eligible to participate. While our primary target is agencies with between 50 and 300 employees, EMS agencies that employ less than 50 personnel or more than 300 will also be eligible to participate.

EMS operations that deploy EMS crews using ground-based ambulance services

will be eligible to participate. Dual ground-based and air-medical organizations will also be eligible, yet organizations that are exclusively air-medical are excluded. The study team will seek to achieve a sample of EMS agencies with goal enrollment based on these agencies being from all four major U.S. Census regions (Midwest, Northeast, South, and West), and inclusion of agencies that operate as dual fire and EMS systems.

Exclusion criteria for EMS agencies:

- 1: operate air-medical operations only
- 2: prohibit EMS personnel from using cellular/mobile, smartphones during shifts
- 3: prohibit EMS personnel from viewing study related materials (education materials) during shift work
- 4: agencies that do not operate within the United States

Inclusion criteria for individual EMS personnel:

- 1: 18 years of age or older
- 2: Currently working as an EMS clinician
- 3: Working a minimum of one shift a week
- 4: Working & residing in the United States
- 5: Working at one of the EMS organizations that agreed to participate in this study
- 6: Have a cellular, mobile, or smartphone that can send and receive text messages
- 7: Willing to answer online surveys and respond to text-message queries for seven days in a row every third week of the month for a total of 24 weeks/6 months

Exclusion criteria for individual EMS personnel:

- 1: Individuals <18 years of age
- 2: Not currently working as an EMS clinician
- 3: Does not work a minimum of one shift a week
- 4: Does not work and/reside in the United States
- 5: Does not work at one of the EMS organizations that agreed to participate in this study
- 6: Does not have a cellular, mobile, or smartphone that can send and receive text messages
- 7: Is not willing to answer online surveys and respond to text-message queries for seven days in a row every third week of the month for a total of 24 weeks/6 months.

Children will not be enrolled in this study. EMS organizations employ licensed/certified EMS clinicians. In order to be an EMS clinician licensed or certified by states within the United States, individuals must be 18 years of age or older.

Power analysis:

With a 40 total EMS agencies enrolled (20 intervention and 20 wait-list control), and with a minimum of 10 participants per agency completing the study, we have 88% power to detect 0.4 standard deviation difference in the mean PSQI. With this level of enrollment, we have 90% power to detect a 20% difference in self-reported fatigue as measured by the CFQ.

We assume that greater than 200 EMS agencies will express interest in this study. We assume that a large proportion (~65%) may express interest, yet will be unable or unwilling to participate for various reasons. We assume that among those EMS agencies that have agreed to enroll and participate, approximately 50% of the individuals at those agencies will agree to enroll and participate. With n=40 EMS agencies and an estimated ~n=50-to-100 individuals at those agencies willing to participate, we anticipate between 1,500 and 3,000 will agree to enroll. We will cap enrollment of EMS agencies to n=40 total agencies and seek to enroll a minimum of n=10 individuals per agency. With these numbers as our goals, we will achieve our goals for the power calculation outlined above.

Preliminary Data Source:

Statistical analysis plan

Intention to treat principles will be used for primary analyses. Descriptive statistics will be used without adjustment for agency-level clustering, and t-tests, tests of medians, chi-square tests, and Fisher's exact tests will be used to examine differences in EMS agency (cluster) and individual participant characteristics by IAI and WLC group status.

Hierarchical mixed effects models with random intercepts will be used for hypothesis testing and to test the impact of the intervention on outcomes. This approach will account for clustering at the agency level (nesting participants within agencies), and account for the dependence between repeated measures at the participant level.

Per-protocol analyses will be used to determine if variation in exposure to the intervention materials (education modules) is associated with a change in outcomes of interest. Hierarchical mixed effects models will be used to account for clustering at the agency level and the dependence between repeated measures at the participant level to characterize the relationship between exposure to the education module intervention and the outcomes of interest among participants who engage with the intervention and had an outcome assessment after intervention exposure. We will use Bonferonni corrected p-values when multiple comparisons are examined to test a study hypothesis. All

analyses will be performed with the SAS statistical software version 9.4 (Cary, North Carolina).

Research activities:

We will begin recruitment by disseminating the EMS Agency Flyer (paper-based version initially) to various EMS agency email listservs and distribution lists (e.g., ask the National Association of State EMS Officials to email their agency members).

Next, we will screen EMS agencies that respond to our study flyers to determine eligibility.

All EMS agencies will be randomized to either the intervention group or the wait-list control group. All agencies and individuals affiliated with the agencies randomized to the intervention group will have access to the study educational materials on the study website (<https://www.emssleephealth.pitt.edu>) once the individuals create their own account. All individuals randomized to the wait-list control group will receive access to the study educational materials - which are accessible on the study website.

Next, we will ask the EMS administrators to circulate a paper-based Research Study Flyer directly to the individual EMS clinicians using email and direct person-to-person distribution - AND -- to circulate a video-based version of the Research Study Flyer.

Next, we will instruct the individuals to visit our study designated website and follow the steps for screening (<https://www.emssleephealth.pitt.edu>). If after following the steps for screening the individual is eligible, he/she will then follow the instructions on the website for enrollment.

All enrollment procedures will take place on the study website (<https://www.emssleephealth.pitt.edu>). First, the individual EMS clinician will be taken to the video-based consent webpage. There he/she will play the consent video and then decide if he/she wants to follow through with enrollment. If he/she decides to enroll, then he/she will click on "(I ACCEPT) I have watched the informed consent video and agree to participate." OR - if he/she decides NOT to enroll, then he/she will click on the second option: "I DO NOT ACCEPT and do NOT want to participate in this research study."

For those who ACCEPT, they will then be taken to a new webpage on the study website that ask if they agree that all of the criteria for enrollment are TRUE. These criteria include all of the items asked on the screening page. This added step will provide final confirmation that the person signing up meets all criteria for enrollment.

For those who agree that all are TRUE, they will be taken to a webpage where they will type/enter in the name of their EMS Agency, their cellular/mobile phone number, and email address. Our study website is designed to cross-validate the agency name against a list that we maintain of EMS agencies that have agreed to participate. This verification takes place in real-time.

The individual's cellular/mobile phone number and email address will be used to

[1] get the individual EMS clinician registered with our automated text-messaging data collection system developed internally by the WPIC Office of Academic Computing;

[2] to email the individual a paper-based copy of the consent documentation; and

[3] to email the individual his/her temporary password to use when first logging into the study website where he/she will create a unique account and personalized password.

Next, the individual will receive four welcome text messages that say: "Welcome to the EMS Sleep Health Study" "You should receive an email with your password and instructions very soon." "REMEMBER: DON'T TEXT WHILE DRIVING." "If you received this message in error, please reply with one word: STOP."

Next, the participant will begin to answer the baseline survey located on the study website.

Once the baseline is complete, the participant will be instructed to visit the shift schedule calendar component of the study website and enter in his/her shift schedule starting on the first Sunday following enrollment and include any shifts during a 7 consecutive days. This action will inform the automated text-message system to send the participant unique text-message based queries daily over a 7 consecutive days. After those 7 consecutive days, he/she will not receive any text messages for two full weeks (minus a few reminder text messages). This process of one week with text message queries followed by two weeks with no text message queries will be repeated for the duration of the study (6 months).

As described above, all individuals affiliated with EMS agencies randomized at baseline to the intervention group will have access to the study materials following completion of the baseline survey -- available on the study website. All individuals affiliated with EMS agencies randomized to the wait-list control group will have access to the study intervention materials at 3 months.

Consent procedures

Waiver to document consent approved.

Potential participants will view the video-based consent materials that will be made available on the study designed website.

Potential participants will be allowed to rewind and watch the consent video multiple times if needed. They can also email or call the study team prior to selecting the ACCEPT or DO NOT ACCEPT options for consent.

Our consent video will provide a detailed description of the study. Potential participants will be allowed to rewind the video and watch multiple times. They can also communicate directly with the study team via email or telephone prior to deciding to ACCEPT or DO NOT ACCEPT consent.

We have also added the screening items to appear one more time after the individual watches the consent video. He/she must then CONFIRM that all of the screening items / eligibility criteria are TRUE. This added step will help to ensure the potential participant is aware of the study criteria.

Our study is nationwide, which makes it difficult to obtain written informed consent from all study participants. We will still obtain consent from the study subjects via a video-based procedure, which does not increase risk.

Data safety monitoring

Our study team will report on progress with recruitment, enrollment, data collection, and any unexpected issues to the Department of Emergency Medicine's Departmental Clinical Research Meeting (DCRM).

Protecting privacy

Only members of our research team are involved in this study protocol. No research findings will be provided to participant family members, insurance companies, employers, or any third party without the participant's authorization. All data that we collect for this research study will be assigned an ID number when received by our computerized data collection system. We will maintain a data file that contains the participant's name, mobile telephone number, and email address. This file will be located on a computer server and kept separate from the other data. This file will be password protected and access to this file will be restricted to core members of the research team. We will publish the study findings in aggregate in peer-reviewed medical journals.

Termination, withdrawal, or attrition

If a participant has not responded to study related text messages over multiple weeks, the study team will attempt to contact the participant to determine if he/she is still participating. If the attempts to contact the participant are unsuccessful, the participant may be classified as "withdrawn" or "lost to attrition," and his/her account on the study website will be suspended.

If a participant withdraws from the study, we will reach out to the participant with a standard email or telephone call. That email or telephone call will [1] acknowledge the participant's withdrawal; [2] thank the participant for his/her time commitment to the study period to withdrawing; and [3] extend an offer to the participant to contact the study team any time with questions. Our study does not have a category of partial withdrawal.

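### The plan's only multiplicity rule is Bonferroni and may or may not cover the two primary outcomes; naming them as one family tested by Holm is a cheap improvement

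*Combined protocol and SAP*

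**What the plan says.** Under Specific Aims: "The study's two primary outcomes of interest include: [1] sleep quality as measured by the Pittsburgh Sleep Quality Index (PSQI"; the second is fatigue on the CFQ. The paragraph on primary and secondary outcomes says that the study is powered for both.

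The Power analysis section assumes 20 agencies per arm and "a minimum of 10 participants per agency completing the study". On that basis it states "we have 88% power to detect 0.4 standard deviation difference in the mean PSQI" and "we have 90% power to detect a 20% difference in self-reported fatigue as measured by the CFQ". It gives no alpha, no sidedness, no intracluster correlation (ICC) and no multiplicity adjustment.

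The only multiplicity rule is one sentence near the end of the Statistical analysis plan, straight after the per-protocol analysis: "We will use Bonferonni corrected p-values when multiple comparisons are examined to test a study hypothesis". It does not name PSQI or CFQ, define a family or give a family-wise alpha. Nothing in the document says whether success needs one primary outcome or both.

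**The concern.** The sentence can be read in two ways, and each has a cost.

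- **PSQI and CFQ form one family.** Each is then tested at half the overall alpha. Holm gives the same protection with no added assumptions. It compares the smaller p-value with 0.025 and, if that is significant, the larger with 0.05. It rejects everything that Bonferroni rejects and sometimes more. When both effects are real, Bonferroni is more likely to miss one of them.
- **Each outcome is its own study hypothesis.** The rule then does not apply between them, and both are tested at full alpha. No power is lost, but nothing limits the chance of a false claim on at least one primary outcome.

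The two costs belong to different readings and cannot both occur. As written, the choice between the readings could be made after the results are known.

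**Working it through.** **Inputs from the document.** Two primary outcomes; 20 agencies per arm; 10 completers per agency, so 200 per arm; 88% power for 0.4 SD on PSQI; 90% power for a 20% difference on CFQ; 1500 subjects in total (Study design).

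**Assumptions, because the document is silent.** Two-sided tests; family-wise alpha 0.05; the stated powers computed either at 0.05 (case 1) or at 0.025 (case 2) per outcome; correlation between the two test statistics from 0 to 0.7 (0 to 0.8 in case 2).

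**1. The plan's own figure.** The effective number per arm is 200 / (1 + 9 × ICC). With ICC 0, power for 0.4 SD is 97.9% at 0.05 and 96.1% at 0.025. The stated 88% is matched by ICC 0.070 at 0.05 (0.061 with a t distribution on 38 df), or by ICC 0.041 at 0.025 (0.031 with t). The 88% can therefore be neither confirmed nor refuted. The CFQ figure cannot be recomputed, because no SD or base rate is given.

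**2. Case 1 by hand, normal approximation, correlation 0.**

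- Bonferroni, PSQI: Φ(1.960 + 1.175 − 2.241) = Φ(0.894) = 81.4%.
- Bonferroni, CFQ: Φ(1.960 + 1.282 − 2.241) = Φ(1.001) = 84.1%.
- Holm, PSQI: 0.814 + (0.880 − 0.814) × 0.841 = 87.0%.
- Holm, CFQ: 0.841 + (0.900 − 0.841) × 0.814 = 88.9%.
- Both, Bonferroni: 0.814 × 0.841 = 68.5%.
- Both, Holm: 0.880 × 0.900 − (0.880 − 0.814) × (0.900 − 0.841) = 78.8%.
- At least one, either method: 1 − 0.186 × 0.159 = 97.0%.

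**3. Simulation at 10 completers per agency.** Case 1 uses t statistics on 38 df with correlation 0 to 0.7. Case 2 uses the normal approximation with correlation 0 to 0.8.

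| | Bonferroni | Holm |
|---|---|---|
| Case 1: PSQI | 81% | 86–87% |
| Case 1: CFQ | 84% | 87–89% |
| Case 1: both | 67–73% | 79–82% |
| Case 1: at least one | 91–97% | the same |
| Case 2: PSQI | 88% | 91–92% |
| Case 2: CFQ | 90% | 92–94% |
| Case 2: both | 79–84% | 87–90% |
| Case 2: at least one | 94–99% | the same |

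In case 1 the gain is about 4 to 6 points per outcome and 9 to 11 for both. With both nulls true, the two methods have the same family-wise error (4.4–4.9% over correlations 0.7 to 0). If only PSQI responds, Holm adds under 0.2 points.

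**4. More completers per agency.** With m completers, the noncentrality is multiplied by √[(m/10) × (1 + 9 × ICC) / (1 + (m − 1) × ICC)]. The planned total gives 1500 / 40 = 37.5 per agency before attrition. In case 1, with the implied ICC of 0.061 used for both outcomes:

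| Completers per agency | Gain per outcome | Both: Bonferroni to Holm |
|---|---|---|
| 10 | 4–6 points | 67–73% to 79–82% |
| 20 | 2–3 points | 88–90% to 94% |
| 37.5 | about 1 point | 96% to 98% |

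In case 2 the gain for both is about 1.5 to 2 points at 20 completers, and gains are 0.2 points or less at 37.5.

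**5. The other reading: no correction between PSQI and CFQ.** With independent tests at 0.05 each, family-wise error is 1 − 0.95² = 9.75%. Over correlations up to 0.7 it is about 8 to 10%.

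**The case against.** Bonferroni is a valid, prespecified method, and nothing in the plan is incorrect because it uses it. A reader might infer that the plan applies Bonferroni to PSQI and CFQ and so loses power. The sentence does not say that: it speaks of multiple comparisons within a study hypothesis and follows the per-protocol text. The Hypothesis heading under Specific Aims carries no text in the copy reviewed, possibly lost in extraction, so it cannot settle what counts as one hypothesis.

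The gain also has limits. It needs real effects on both outcomes, it leaves power for at least one outcome unchanged, and its larger values belong to the 10-per-agency minimum. At the planned total of 1500 it is about 2 points or less, although attrition is not stated and could move the trial back towards the minimum. Calling the uncorrected family-wise error nearly doubled fits only near-zero correlation; at the lower end of the range it is about 1.6 times 5%.

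Finally, deleting the sentence would remove the plan's only rule for other multiple comparisons. All of these objections stand. They limit the point's size and shape the fix. They do not remove the ambiguity, nor the fact that Holm is at least as powerful for any family that the sentence covers.

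**Conclusion.** The point holds as a low-cost improvement. The document should settle whether PSQI and CFQ form one family, and Holm is the better method if they do. That preference does not depend on the unstated alpha, ICC or correlation; only the size of the gain does.

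At 10 completers per agency, with both effects real and the stated powers computed at two-sided 0.05, Holm adds about 4 to 6 points per outcome and 9 to 11 for both. If the stated powers were computed at 0.025, it adds about 2 to 4 points per outcome and 5 to 8 for both. If the outcomes are not one family, there is no power to recover, and the issue is a family-wise error of about 8 to 10%.

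A reader might also infer that the stated 88% power is wrong. That is not supported: plausible ICC values reproduce it at either alpha.

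**What to change.** Keep the existing sentence for other multiple comparisons, but change Bonferroni to Holm, and add:

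> The two primary hypotheses (PSQI and CFQ, intervention versus wait-list) form one family tested by Holm's procedure at two-sided 5%; the smaller p-value is compared with 0.025 and, if significant, the larger with 0.05.

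State the alpha at which the 88% and 90% power figures hold. The added sentence does not fix the time point of the comparison. The SAP should name it, since the wait-list group gains access to the materials at 3 months.

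The cost is SAP wording only. SAS 9.4, already the named software, provides Holm-adjusted p-values, and no extra data or participants are needed. The one drawback is that simultaneous confidence intervals are less simple under Holm, so show 97.5% intervals for each primary outcome alongside the Holm results.

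### Participant characteristics are compared by arm with tests that ignore agency clustering, so their p-values are too small; the role of baseline scores and the concealment of arm during staff recruitment are also left unstated

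*Combined protocol and SAP*

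**What the plan says.** **Tests of participant characteristics.** The section Statistical analysis plan says that descriptive statistics carry no adjustment for agency. The same sentence names t, median, chi-square and Fisher tests for comparing both agencies and individual participants by arm. The agency is the unit of allocation: "All EMS agencies will be randomized to either the intervention group or the wait-list control group" (Research activities).

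**Primary model.** The same section specifies random-intercept mixed models that nest participants in agencies and allow for correlation among a participant's repeated measures. It lists no fixed effects and gives baseline PSQI or CFQ no stated role. Primary and secondary outcomes speaks of power to detect change; Power analysis speaks of a difference in mean PSQI.

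**Order and access.** Research activities moves from randomising agencies to recruiting staff: "Next, we will ask the EMS administrators to circulate a paper-based Research Study Flyer directly to the individual EMS clinicians". Online screening, consent and enrolment follow, and then "Next, the participant will begin to answer the baseline survey located on the study website". Study design says only: "We will use an experimental study design with randomization at baseline and use of a wait-list control group". On access, Research activities first says that staff of intervention agencies have it "once the individuals create their own account", and later that they "will have access to the study materials following completion of the baseline survey". Wait-list staff "will have access to the study intervention materials at 3 months".

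**The concern.** Forty agencies are allocated, not 400 or 1,500 independent people. Where staff of one agency resemble each other, a test that treats them as independent understates the standard error, and chance differences between agencies are reported as significant imbalance too often. This is also the table in which a reader would look for signs of uneven recruitment, so false signals there can mislead.

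The primary model raises a different question. Follow-up-only, change and baseline-adjusted analyses all fit the present wording. They differ in precision and, if enrolment depended on arm, in bias.

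Enrolment could depend on arm because agency randomisation protects the comparison of individuals only when who enrols is unrelated to arm. Power analysis expects about half of the staff to take part, which leaves room for uptake to differ.

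**Working it through.** **Step 1: the plan's own power figure.** Inputs from Power analysis: 20 agencies per arm, 10 completers each, a 0.4 SD difference in PSQI, 88% power. The alpha, sidedness and ICC are not stated.

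Without clustering, SE = sqrt(2/200) = 0.100 and power = Φ(0.4/0.100 − 1.96) = 97.9%, so the 88% is not an unclustered figure. With clustering and no baseline adjustment, SE = sqrt[(2/20) × (ICC + (1 − ICC)/10)]. At ICC 0.070 the SE is 0.128 and power is Φ(3.13 − 1.96) = 88%. Solving for 88% under each convention:

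| Test level | Normal | t, 38 df |
|---|---|---|
| two-sided 5% | 0.070 | 0.061 |
| two-sided 2.5% (Bonferroni, two outcomes) | 0.041 | 0.031 |

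A one-sided 5% test would imply about 0.11; that variant is left out below. The working range is 0.03 to 0.07.

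**Step 2: true error of an unclustered test at nominal 5%.** Error = 2 × [1 − Φ(1.96/sqrt(DE))], with DE = 1 + (m − 1) × ICC. The cluster size m is 10 (Power analysis) or 1500/40 = 37.5 (total enrolment in Study design, over 40 agencies). For example, ICC 0.070 and m = 10 give DE = 1.63, 1.96/1.277 = 1.535, and 12.5%. The table uses unrounded ICCs.

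| ICC | m = 10 | m = 37.5 |
|---|---|---|
| 0.031 | 8.3% | 18.0% |
| 0.041 | 9.4% | 21.6% |
| 0.061 | 11.5% | 27.4% |
| 0.070 | 12.5% | 29.8% |

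Simulated t-tests with 20 v 20 agencies at ICC 0.03, 0.06 and 0.07 reject in 8.6%, 11.8% and 13.2% of runs (m = 10) and in 18.5%, 29.0% and 30.5% (m = 38), in line with the formula. At an ICC of only 0.01 the formula gives 6.0% and 9.3%.

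**Step 3: precision of the primary contrast, with no selection.** Let ρ be the baseline to follow-up correlation, assumed 0.5 to 0.8 and equal at agency and person level. Relative variances are 1 (follow-up only), 2(1 − ρ) (change) and 1 − ρ² (adjusted).

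| ρ | Follow-up only | Change | Adjusted |
|---|---|---|---|
| 0.5 | 1 | 1.00 | 0.75 |
| 0.8 | 1 | 0.40 | 0.36 |

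Adjustment therefore saves 25% to 64% against follow-up only. Against change the ratio is (1 + ρ)/2, a saving of 25% at ρ = 0.5 and 10% at ρ = 0.8.

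**Step 4: bias if enrolment depended on arm (illustration only).** Assume that intervention agencies enrol 60% of poor and 40% of good sleepers and wait-list agencies 50% of each. The mean shift among those enrolled is s = 0.2 × sqrt(2/π) = 0.160 SD. If selection acts on the measured score, the biases are ρs, −(1 − ρ)s and 0. If it acts on underlying sleep quality, they are sqrt(ρ)s, 0 and (1 − ρ)sqrt(ρ)s. Positive values count against the intervention; units are SD.

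| Selection on | ρ | Follow-up only | Change | Adjusted |
|---|---|---|---|---|
| measured score | 0.5 | 0.080 | −0.080 | 0 |
| measured score | 0.7 | 0.112 | −0.048 | 0 |
| measured score | 0.8 | 0.128 | −0.032 | 0 |
| underlying quality | 0.5 | 0.113 | 0 | 0.056 |
| underlying quality | 0.7 | 0.134 | 0 | 0.040 |
| underlying quality | 0.8 | 0.143 | 0 | 0.029 |

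Neither change nor adjustment is unbiased under both models. Follow-up only has bias under both.

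**The case against.** **The tests are descriptive.** The plan is open that these summaries are unadjusted, ties no decision to them, and handles clustering in the primary model. That stands, and it limits the consequence to the descriptive tables. It does not make the p-values correct. The ICC in Step 1 is also one implied for PSQI, and other characteristics may cluster more or less. A reader might infer that the trial's hypothesis tests share the fault; they do not, and neither do the agency-level comparisons.

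**Baseline may already be in the model.** The reference to repeated measures may mean that baseline is one of the outcomes, with an arm-by-time term. This stands as a possible reading, but the plan does not say so. A reader might infer that baseline is ignored and that the effect could be off by 0.14 SD, or 0.143/0.4 = 36% of the design difference. The documents do not support that. The figure applies only to a follow-up-only model, at ρ = 0.8, under an enrolment split with no basis in the text. On the arm-by-time reading the change column applies instead. Staff also enrol before answering the baseline survey, which makes selection on underlying sleep quality the more natural model, and there change is the contrast without bias.

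**No disclosure of arm is shown.** A reader might infer that staff enrol knowing their arm. The documents do not show it. The website takes the agency's name only after consent, and the later access statement releases materials after the baseline survey. Recruitment methods has flyers going out once an agency agrees, with no randomisation step between. Payments and education credit are common to both arms, and Study design says "This design will ensure that all study participants receive the intervention", which reduces the incentive. What remains is that nothing withholds the arm: administrators distribute the flyers, prospective participants may contact the study team before accepting, and one access statement ties access to account creation, not to the baseline survey.

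**Conclusion.** The unclustered tests of participant characteristics are wrong as written. At the ICC of 0.03 to 0.07 implied by the plan's own power statement, a nominal 5% test errs 8.3% to 12.5% of the time with 10 per agency and 18.0% to 29.8% with 37.5. This rests on a two-sided 5% or 2.5% test, no baseline adjustment in the power calculation, and an ICC for other characteristics similar to that for PSQI.

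The handling of baseline is an omission that is cheap to repair. The gain is 25% to 64% of the variance only if the alternative is follow-up only, and 25% down to 10% if it is a change contrast.

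The recruitment point is conditional. The order listed in Research activities puts randomisation before staff recruitment, but Recruitment methods and the references to randomisation at baseline leave it uncertain. The plan permits enrolment to depend on arm; it does not show that it does.

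**What to change.** 1. For individual characteristics, report standardised differences without p-values, or use models with an agency random intercept. Leave agency-level comparisons as they are. This is a wording change.

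2. State the fixed effects of the primary models. Prespecify that baseline is used and that a follow-up-only comparison is not primary: for example, baseline PSQI or CFQ as a covariate, with the change (arm-by-time) contrast as a prespecified sensitivity analysis, both reported. No new data are needed if the baseline survey holds both scales; its contents are not listed, but the plan's reference to change suggests that it does. The drawback is that, if enrolment depends on arm through underlying sleep quality, the adjusted estimate keeps a bias of 0.03 to 0.06 SD under the 60/40 split, while the change contrast has about none. If it depends on the measured score, the reverse holds.

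3. State whether randomisation precedes staff recruitment. Instruct the study team not to disclose the arm to administrators or prospective participants before each person's consent and baseline survey, and report uptake by arm and agency. This costs little, but colleagues may still pass the arm on by word of mouth, and equal uptake would not rule out different composition.

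4. Reconcile the two access statements in Research activities (on account creation; after the baseline survey). Item 3 depends on how this is settled.
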